11.3. GENOTYPING

The primary analyses of the primary efficacy endpoint will be performed on the following genotype subgroups of interest, which are determined once, at Baseline, with a blood test: HLA typing, presence of BDNF (Brain derived neurotrophic factor) mutation, and ApoE locus.

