18.2.1.4 Subgroup Analysis

Inferential analyses will be performed on some subgroups of interest. Details of the subgroup analyses will be included in the SAP.

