3.5. DETERMINATION OF SAMPLE SIZE

The sample size was estimated based on the primary efficacy endpoint, proportion of responders, which is defined as ≥ 10 points improvement from baseline on the Fugl-Meyer Motor Scale (FMMS) motor total score, at Month 6 Last Observation Carried Forward (LOCF). Based on the results of the Phase 1/2a study it was assumed that the responder rate was 33% for the SB623 treatment group.

Given high surgical placebo response rates, it was assumed that the responder rate in the surgical sham was 11.7% (i.e. 35% of the treatment responder rate). Assuming an 80% power, alpha level of 0.05 (two-tailed test), and 2:1 (pooled SB623 treatments: control) ratio of randomization, a sample size of 138 (92 subjects in treatment group and 46 subjects in control group) is required to detect this 21.3% difference in the proportion of responders. Based on a 10% upward adjustment to compensate for dropout subjects, a total of approximately 156 subjects (104 treatment and 52 controls) will be required.

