A GLMM model will be utilized using the mITT population as primary analysis. The GLMM model will have the outcome variable, FMMS responder (either \geq or $<$ 10 points improvement in FMMS), and independent variables of treatment, visit, treatment and visit interaction, and pooled surgical site as effects, and baseline FMMS motor total score and baseline mRS score as covariates. Treatment, visit, and pooled surgical site will be treated as categorical variables. Visit will be fitted as a repeated effect within subject. Link function will be set to logit and distribution to binary. An unstructured variance-covariance structure will be used. If this fails to converge then the following variance-covariance structures will be used based on the step-down order until model convergence is obtained: heterogeneous Toeplitz, heterogeneous autoregressive, heterogeneous compound symmetry, and then compound symmetry. The Kenward-Roger method will be used to estimate the denominator degrees of freedom. Adjusted odds ratios and 95% CIs for each visit will be presented for combined SB623 versus sham control. A separate analysis will be repeated for the comparisons of each SB623 group versus sham control for FMMS response. A forest plot of odds ratios and 95% CIs will be presented for individual/combined SB623 versus sham control. The results for Month 6 will be the primary interest.

For FMMS response, a supportive analysis will also be conducted based on the per protocol population using the same statistical method and following the same process for selection of variance-covariance structure.

A logistic regression analysis will be conducted by visit to include FMMS response as outcome variable, and independent variables of treatment and pooled surgical site as effects, and baseline FMMS motor total score and baseline mRS score as covariates. Odds ratios and 95% CIs will be reported for each visit.

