9.3. OTHER EFFICACY ANALYSIS

Graphs will be presented summarizing the LS mean value over time by treatment group (pooled SB623, individual SB623 groups and sham control) for the following variables: change from baseline in FMMS total score, changes from baseline in the two NeuroQOL

INC1005439

Sponsor: San-Bio, Inc.

Protocol: SB-STR02

Final 1.0

Statistical Analysis Plan

subdomain T scores. The graphs will plot the LS mean (\pm standard error) over time. The graphs will also present the p-value at each post-baseline timepoint from the MMRM model comparing each SB623 group with sham control.

The following subgroup analyses will be performed for the primary endpoint:

- Baseline FMMS motor total score: (0 - 34, 35 -67, 68 - 100)
- Baseline FMMS motor total score: (0 - 50, 51- 100)
- Age group: ≥ 55 and < 55 years
- Age group: 18 to < 50 and 50 to 75
- Gender
- Race: White and other races
- Length from the last stroke: 6-12, >12 -24 and >24 months
- Stroke location: Subcortical grey matter; subcortical white matter; cortical frontal; cortical temporal; cortical parietal; cortical other
- Cerebral infarct size: < 50 , 50 - 75, >75 - 100 and >100 -150 cm^3
- Compliance with the physical therapy throughout the study: yes ($\geq 80\%$ of all tasks) or no
- Baseline mRS score: 2, 3 and 4
- The primary efficacy endpoint will also be summarized by viable cell/mL and by percentage cell viability (\leq sample median value vs. $>$ sample median value). These subgroup analyses will be done for the SB623 doses only.

Subgroups with total number of subjects less than 10 will be combined into a single subgroup.

Statistical Analysis Plan

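### The genotype subgroup analyses apply the primary model to subgroup categories with no treatment-by-subgroup interaction and no fallback for sparse data, and SAP 9.3 names no subgroup model

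*SAP*

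**What the plan says.** Protocol 18.2.1.4 says "Inferential analyses will be performed on some subgroups of interest" and leaves the details to the SAP.

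SAP 11.3 supplies a method for the genotype variables: "The primary analyses of the primary efficacy endpoint will be performed on the following genotype subgroups of interest". The categories follow: three for HLA mismatch (11.3.1), two for BDNF (11.3.2) and two for ApoE (11.3.3). SAP 11.1 and 11.4 use the same form of words for the head MRI and antibody subgroups.

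The analysis referred to is the GLMM of SAP 9.1.1, with "independent variables of treatment, visit, treatment and visit interaction, and pooled surgical site as effects, and baseline FMMS motor total score" and baseline mRS as a second covariate. It starts from an unstructured covariance over the post-baseline visits. If it does not converge, simpler covariance structures are tried in a fixed order. Nothing is said about sparse or empty cells in the fixed effects. Section 9.1.1 also plans a logistic regression by visit with treatment, pooled site and the same two baseline covariates.

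SAP 9.3 lists subgroups for the primary endpoint (baseline FMMS, age, sex, race, time since stroke, stroke location, infarct size, physical-therapy compliance, baseline mRS) and names no model. Its one size rule is "Subgroups with total number of subjects less than 10 will be combined into a single subgroup". Tables 14.2.1.3 to 14.2.1.7, which hold these subgroups, have titles that mention response-rate summaries only.

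No treatment-by-subgroup term appears in the protocol, the SAP text, the table list or the sample code in SAP Appendix I, where the only interaction is treatment by visit.

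**The concern.** A genotype analysis is meant to show whether the treatment effect depends on genotype. Applying the primary model to each category gives one odds ratio and one p-value per category and no test of the difference between them. The natural reading of such a table, that treatment worked in one genotype and not in the other, is then driven largely by category size and chance.

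There is also a practical problem. A model sized for the full trial, with a term for every pooled site, is carried over to subsets in which the sham arm may have very few responders or none. The step-down in covariance structure does not help with that. What would be reported for a category without a finite odds ratio is left open, and the choice would be made after unblinding.

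For the 9.3 subgroups the gap is different: the protocol promises inference on some subgroups, and the SAP does not say which of these are to be tested or how.

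**Working it through.** **Inputs.** All come from SAP 3.5: planning responder rates of 33% on SB623 (both doses pooled) and 11.7% on sham; two-sided alpha 0.05 with 80% power; two treated subjects per sham subject; 92 + 46 = 138 evaluable, raised for dropout to about 156 (104 + 52).

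**Reproducing the plan's figure.** Pooled responder rate (2 × 0.33 + 0.117)/3 = 0.259. Sham n = [1.96 √(0.259 × 0.741 × 1.5) + 0.8416 √(0.33 × 0.67/2 + 0.117 × 0.883)]² / 0.213² = (1.0516 + 0.3892)²/0.04537 = 45.8, so 46 sham, 92 treated, 138 in all. With 10% dropout, 46/0.9 = 51.1, rounded up to 52, and 3 × 52 = 156. Both figures agree with the SAP.

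**Can within-subgroup p-values show a difference?** Suppose the true effect is 33% against 11.7% in both halves of 156 (52 treated and 26 sham in each).
- Power in one half: SE under the null = √(0.1919 × (1/52 + 1/26)) = 0.1052. SE under the alternative = √(0.2211/52 + 0.1033/26) = 0.0907. Power = Φ((0.213 − 1.96 × 0.1052)/0.0907) = 0.53.
- Chance that exactly one half is significant = 2 × 0.53 × 0.47 = 0.50.
- For a 30:70 split the powers are 0.325 and 0.693, giving 0.57. For 20:80 they are 0.215 and 0.757, giving 0.65.

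**Size of the model.** SAP Table 3 lists four pooled sites (14 + 13 + 12 + 16 = 55 subjects). The other 156 − 55 = 101 subjects sit in sites of 12 or more, so there are at most 8 further levels (101/12 = 8.4) and 12 in all. With an assumed 11 levels, the fixed effects number 1 + 1 + 4 + 4 + 10 + 2 = 22 (intercept, treatment, visit, treatment by visit, site, covariates). Five visits give 5 × 6/2 = 15 unstructured covariance parameters.

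**How often is the Month 6 odds ratio infinite?** The documents give no subgroup sizes, so n is an assumed range. Subjects were drawn at random from 156 in 11 sites (the four of Table 3 plus seven assumed sites of 14 or 15), with 2:1 allocation and the planning rates. The site-adjusted odds ratio is infinite or zero when the number of treated responders sits at its largest or smallest possible value given the site totals. This mirrors the by-visit logistic regression without its two covariates. Ranges show two separate runs. The last column is 0.883 raised to the number of sham subjects (n/3).

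| Subgroup n | No finite site-adjusted Month 6 odds ratio | No sham responder at all |
|---|---|---|
| 30 | 45–46% | 29% |
| 60 | 11% | 8% |
| 78 | 4–5% | 4% |
| 104 | about 1% | 1% |

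For the repeated-visit GLMM, a separation check of the fixed effects (6 to 12 site levels, latent visit correlation 0.5 or 0.8, independence likelihood) found at least one non-finite coefficient in 75–99% of trials at n=30, 12–56% at n=78, 3–24% at n=104 and 0–3% at n=156. Above about n=50 most of these are site or other nuisance terms and not the treatment contrast.

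**What an interaction test could detect.** The variance of the difference between two subgroup risk differences at N=156 is (0.2211/104 + 0.1033/52)/(f(1 − f)), where f is the fraction in the smaller category. At f = 0.5 the SE is 0.128 and the power for a 21.3-point difference is Φ(0.213/0.128 − 1.96) = 38%. At f = 0.3 it is 33% and at f = 0.2 it is 26%. The differences detectable with 80% power are 36, 39 and 45 points.

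**The case against.** The strongest reply is that this is exploratory work. Genotype outcomes are exploratory endpoints in SAP 4.3, the analyses sit under SAP section 11, and the primary result does not depend on them. That is right and limits the weight of the point. It does not supply the missing comparison.

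A reader might infer that all subgroup effects in this trial come from refitting the full primary model inside each category. The documents do not support that. Section 9.3 states no model and its table titles look descriptive, so the defect there is an unspecified method. Even in 11.3 the text does not say that the fits are separate, and the title of Table 14.2.9.1 names no model; the within-category fit is the plain reading because no other method is given. Nor is a count of expected false positives across the 9.3 categories warranted, since no test is specified for them.

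A reader might also infer that the genotype odds ratios will generally not be estimable, down to subgroups of 10. That does not hold either. BDNF and ApoE are already dichotomised, so one level of each has at least half the subjects, about 78 of 156, where the Month 6 odds ratio is almost always finite. The size rule of 10 is written in 9.3, not in 11.3. The infinite-odds-ratio figures describe the by-visit logistic regression; the GLMM shares site effects across visits, so a site without a Month 6 responder can still inform its treatment contrast.

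Finally, an interaction test here has low power. True, and it should be labelled accordingly; low power is also why separate subgroup p-values mislead.

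**Conclusion.** The concern stands in two parts. First, no planned analysis tests whether the treatment effect differs between subgroups, and the output that 11.3 would produce cannot stand in for one: with identical true effects in equal halves, exactly one is significant about half the time. This rests only on the planning rates, N=156 and 2:1 allocation. Second, 11.3 has no rule for sparse fixed effects, which matters for the smaller category. The odds ratio is infinite in about 45% of trials at n=30 and 11% at n=60, but rarely at n=78 or above; this rests on assumed subgroup sizes and 11 pooled sites, seven of them assumed. For 9.3 the conclusion is that the method, and which subgroups are to be tested, are unspecified. The primary analysis is unaffected.

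**What to change.** In SAP 11.3, and in 9.3 for any subgroup to be tested inferentially, fit one model per baseline subgroup variable in the whole mITT set. Take the primary adjustment terms, add subgroup and treatment-by-subgroup with a Month 6 contrast (the Month 6 logistic regression is the simplest vehicle), and report the subgroup odds ratios and the interaction p-value from that model. For the other 9.3 subgroups, say that they are descriptive.

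The single model is not enough alone. In a Month 6 logistic model with 20% of subjects in the smaller category, at least one coefficient is non-finite in 29% of trials with 6 sites and 56% with 12, against 85% and 100% for a separate fit in that category. So also specify:
- a reduced site term or penalized likelihood when data are sparse;
- counts with an exact confidence interval for the risk difference when an arm has no responders;
- merging of adjacent categories only, for ordered variables, in place of one combined group for everything under 10;
- an exploratory label, stating power of about 26–38% for a 21.3-point difference between subgroups.

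An interaction term does not rescue the post-treatment MRI and post-baseline antibody groupings of 11.1 and 11.4; those stay descriptive.

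The cost is SAP wording and one programming macro. The small downside is that site and baseline effects are assumed common across subgroups.

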11.3.1. HLA Genotype

HLA typing compares donor to recipient at each of two alleles for each of the following loci:

- a. HLA-A (0 mismatch, 1 mismatch, or 2 mismatches)
- b. HLA-B (0 mismatch, 1 mismatch, or 2 mismatches)
- c. HLA-C (0 mismatch, 1 mismatch, or 2 mismatches)
- d. HLA-DRB1 (0 mismatch, 1 mismatch, or 2 mismatches)
- e. HLA-DQB1 (0 mismatch, 1 mismatch, or 2 mismatches)

These results generate the following 3 HLA subgroup categories (by adding up the

INC1005439

Sponsor: San-Bio, Inc.

Protocol: SB-STR02

Final 1.0

Statistical Analysis Plan

number of mismatches at each locus), which will be used for the subgroup analyses:

High degree of mismatch (8-10 mismatches)

Moderate degree of mismatch (4-7 mismatches)

Low degree of mismatch (0-3 mismatches)

11.3.2. Presence of BDNF Mutation

For this variable, there are three possible genotype groups.

BDNF Group	Genotype
A	Val/Val
B	Val/Met
C	Met/Met

The subgroup analyses will be performed for the following subgroup categories, which have been dichotomized according to whether the subject has at least one Met allele:

BDNF Subgroup	BDNF Groups
No Met alleles	A
At least one Met allele	B, C

INC1005439

Sponsor: San-Bio, Inc.

Protocol: SB-STR02

Final 1.0

Statistical Analysis Plan

11.3.3. ApoE Genotype

For this variable, the groups are as follows:

Apo Group	ApoE2	ApoE3	ApoE4	Description
A	0	0	2	Homozygous ApoE4
B	0	1	1	Heterozygous ApoE4
C	1	0	1	Heterozygous ApoE4
D	0	2	0	Homozygous ApoE3
E	1	1	0	Heterozygous ApoE2
F	2	0	0	Homozygous ApoE2
Other				None of the above

The subgroup analyses will be performed for the following subgroup categories:

Apo Subgroup	Apo Groups
At least one ApoE4 allele	A, B, C
No ApoE4 alleles	D, E, F, Other

11.4. ANTIBODY VARIABLES

The primary analyses of the primary efficacy endpoint will be performed on the following antibody subgroups of interest:

- Subjects with pre-existing donor-specific antibodies [defined as having any one of the following a) MFI > 1000 for antibodies against donor HLA; b) virtual T cell positive; c) virtual B cell positive] versus no pre-existing donor-specific antibodies.
- Subjects with a significant increase in donor-specific antibodies at any post-baseline visit versus no increase or a non-significant increase at all post-baseline visits

INC1005439

Sponsor: San-Bio, Inc.

Protocol: SB-STR02

Final 1.0

Statistical Analysis Plan

- Subjects with either pre-existing donor-specific antibodies or a significant increase in donor-specific antibodies at any post-baseline visit versus those with neither.

While the subgroup categories in the first bullet represent true subgroups, being defined at baseline, the subgroup categories in the second and third bullets are not true subgroup categories. Subjects that are negative for both Flow PRA Class I and Flow PRA Class II and do not have MFI, virtual T-cell, or virtual B-cell results will be assigned the following values for summaries: a MFI value of < 1000 and Virtual T-cell and B-cell results of 'Negative'.

Descriptive statistics for the FMMS score at Month 6 and the corresponding change from baseline will be presented by treatment group (control, pooled SB623, and each SB623 dose) and subgroup category for each antibody subgroup variable.

For each treatment group (control subjects, pooled SB623 subjects, and each SB623 dose group) and each visit the following results will be presented:

- Number and percentage of subjects positive for flow PRA class I
- Descriptive statistics for percentage PRA class I
- Number and percentage of subjects positive for flow PRA class II reaction
- Descriptive statistics for percentage PRA class II
- Descriptive statistics for MFI value
- Number and percentage of subjects with MFI > 1000
- Number and percentage of subjects with virtual T cell positive
- Number and percentage of subjects with virtual B cell positive
- Number and percentage of subjects with change in donor-specific antibodies in each of the following categories: no increase; increase, not significant; increase, significant. (post-baseline visits only).

Shift tables will be presented showing the number and percentage of subjects in each cross-classification category (baseline versus worst post-baseline visit, where positive and yes are worse than negative and no, respectively) for the following variables:

1. Flow PRA class I (positive or negative)
2. Flow PRA class II (positive or negative)

INC1005439

Sponsor: San-Bio, Inc.

Protocol: SB-STR02

Final 1.0

Statistical Analysis Plan

3. MFI > 1000 (yes or no)
4. Virtual T cell interpretation (positive or negative)
5. Virtual B cell interpretation (positive or negative)

The shift tables will be done for each treatment group (control, pooled SB623, and each SB623 dose).

The number and percentage of subjects with an increase in donor-specific antibodies, either significant or not significant, at any post-baseline visit will be presented by treatment group (control subjects, pooled SB623 subjects, and each SB623 dose group).

INC1005439

Sponsor: San-Bio, Inc.

Protocol: SB-STR02

Final 1.0

Statistical Analysis Plan

12. EXPLORATORY ANALYSIS NOT SPECIFIED IN THE PROTOCOL

Based on the clinical interest, the following analyses for FMMS, ARAT and gait velocity are included in the SAP in addition to the analyses specified in the protocol:

- Descriptive summary for actual and change from baseline
- Change from baseline using MMRM model
- Relationship between Global Rating of Perceived Change and change from baseline in FMMS motor total score to establish clinically meaningful difference level for FMMS
- Change from baseline in FMMS motor total score by subgroups based on volume of FLAIR signal lesion in MRI at day 8 (volume of lesion < median volume of lesion for all subjects, volume of lesion \geq median volume of lesion for all subjects)

INC1005439

Sponsor: San-Bio, Inc.

Protocol: SB-STR02

Final 1.0

Statistical Analysis Plan

APPENDIX I SAMPLE SAS CODE IN STATISTICAL ANALYSIS

- 1) Binary endpoint by generalized linear mixed model:

```
proc glimmix data=dataset order=data;
class treatment visit subjid pooled_site;
model response(event='1')= treatment visit treatment *visit baseline pooled_site/ dist=binary
link=logit ddfm=KR OR;
random visit/subject=subjid residual type=xx;
lsmeans treatment*visit/pdiff cl;
run;
```

- 2) Linear mixed model for repeated measures:

```
proc mixed data=dataset;
class treatment visit subjid pooled_site;
model chg=treatment visit treatment*visit baseline pooled_site /ddfm=KR;
repeated visit/subject=subjid type=xx;
lsmeans treatment*visit/pdiff cl;
run;
```
